3.8.5. Partial Dates for Concomitant Medications

Concomitant therapy start date (references to month are the month of the concomitant therapy start date). Partial date imputation will follow the same pattern as for AEs in section 3.8.4 above.

Concomitant therapy stop date (references to month are the month of the concomitant therapy stop date):

1. If only day is unknown, then set equal to last day of month.
2. If only year is known, assume it is the last day of the year.
3. Otherwise (i.e. day, month and year are missing) leave as missing.

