5.9 Prior and Concomitant Therapies and Medications

5.9.1 Prior and Concomitant COPD Therapies

All prior and concomitant therapies for COPD will be recorded in the eCRF, with the medication, dose, route and start and stop date(s) and time(s) clearly recorded to document all required washout periods and compliance with the Inclusion and Exclusion Criteria.

All patients will be supplied with albuterol/salbutamol to be used as per the discretion of the Investigator. The albuterol/salbutamol can be dosed on a regularly scheduled basis and/or as needed use.

The following medications are restricted or prohibited during the study as indicated:

- Oral therapies for COPD (e.g. oral steroids, theophylline and roflumilast) are not allowed in the 3 months prior to Visit 1 and throughout the study. Oral mucolytics are allowed.
- Terbutaline is not allowed beginning the day prior to Visit 1
- Long acting bronchodilators (LABAs or LAMAs) are not allowed during the study and must be withheld prior to Visit 1 as follows:
 - o Once daily bronchodilators must be stopped at least 48 hours prior o
 Twice daily bronchodilators must be stopped at least 24 hours prior □
 Short acting bronchodilators (albuterol/salbutamol or ipratropium) must be withheld for at least 8 hours prior to spirometry at each study visit. If this withhold is not met, the patent should be rescheduled for a repeat visit within 2 days
- Patients taking inhaled corticosteroids (ICS) may continue their medication only if the dose is stable from at least 4 weeks prior to Visit 1 and is expected to remain stable. Patients taking combination products that include ICS should be prescribed the inhaled steroid at the same or equivalent dose contained in the combination product to allow continuation of steroid use regularly throughout the study. Inhaled steroid medication should be procured via prescription for patients requiring its use; it will not be supplied by the Sponsor

Pulmonary rehabilitation programs should not be started or completed during participation in the study, although an ongoing maintenance program is acceptable in accordance with Exclusion Criterion #9. Oxygen therapy is an exclusion criterion for this study.

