3.8.4. Partial Dates for AEs

Adverse event start date (references to month are the month of the AE start date):

1. If only month and year are known and study medication started during that month then set start date equal to study medication start date.
2. If month and year are known and study medication started prior to or after that month then set start date equal to 1st day of month.
3. If only year is known, and it is the same as study medication start year, assume it is the study medication start date/year. If it is different from study medication start year, assume it is the first day of the year.
4. If full start date (i.e. day, month, and year are missing) is unknown impute start date as the study medication start date. If imputed start date is greater than stop date, it will be imputed as stop date.

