5.6.6. Examination of Subgroups

The following subgroups will be examined:

1. Current vs. ex-smokers
2. Chronic bronchitis vs. no chronic bronchitis at screening
3. Males vs. females.
4. Symptoms severity (MRC <2 vs. MRC \geq 2) at randomization
5. Age: (\geq 65 vs < 65)
6. Inhaled corticosteroid use versus no use (use of medications during the last 7 days of run-in phase).
7. By baseline FEV1 (> or \leq 50% predicted)

Subgroup analyses will be performed for the primary and the selected secondary endpoints (see 5.4).

The MMRM model will be run on each subgroup separately.

6. Safety Endpoints

Safety measures that will be collected and investigated include adverse events (AEs), clinical

laboratory tests, vital signs, physical examination and electrocardiograms assessments (ECGs, 12-Lead and using 24 hour Holter monitors).

All safety analyses will be performed on the safety analysis set. Patients will be analyzed according to the treatment received. All safety summaries will present the five treatment groups.

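### SAP 3.8.5 gives some ongoing medications the first-dose date as their start, so they drop out of the prior-medication tables; for a continuing inhaled steroid that date conflicts with the protocol

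*SAP*

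**What the plan says.** SAP 3.8.5 has its own rules for medication stop dates but none for start dates: "Partial date imputation will follow the same pattern as for AEs in section 3.8.4 above". The rules it points to, in SAP 3.8.4, are:

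- Rule 1: "If only month and year are known and study medication started during that month then set start date equal to study medication start date". Rule 2 sends any other known month to its first day.
- Rule 3: "If only year is known, and it is the same as study medication start year, assume it is the study medication start date/year". Otherwise, "If it is different from study medication start year, assume it is the first day of the year".
- Rule 4: if the full start date "is unknown impute start date as the study medication start date". A cap follows: "If imputed start date is greater than stop date, it will be imputed as stop date".

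SAP 3.8.3 says that dates decide whether a medication is prior, concomitant or both. SAP 4.4 defines prior as use before the first dose, and refers to 3.8.5 for partial dates. SAP 3.7.1 treats a medication that begins on the reference start date as post-baseline.

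Two other places matter for inhaled steroids. Protocol 5.9.1 lets patients stay on them "only if the dose is stable from at least 4 weeks prior to Visit 1". SAP 5.6.6 lists the subgroup "Inhaled corticosteroid use versus no use (use of medications during the last 7 days of run-in phase", with a separate MMRM in each stratum for the primary and the selected secondary endpoints.

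**The concern.** For adverse events, moving an unknown onset to first dose is cautious, because the event then counts as treatment-emergent. For medications the same step works the other way: a drug the patient was already taking appears to begin on Day 1, and its earlier use disappears. The SAP gives no reason for borrowing the rule and makes no exception for drugs already in use at screening.

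At stake are the descriptive prior-medication summaries, including the separate COPD table by therapeutic class, which Protocol 9.2.2.3 lists among the baseline characteristics. The ICS subgroup is also at stake if it is programmed from the same dates. The error has one direction: earlier use is lost, never added.

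**Working it through.** The plan states no figure on this point, so the check runs the written rules on example records.

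**Inputs**
- Start dates: SAP 3.8.4 rules 1 to 4. Stop dates: SAP 3.8.5.
- Prior: start before first dose. Concomitant: start on or after first dose, or an earlier start with no stop date or a stop after first dose (SAP 4.4). A start on the first-dose day is post-baseline (SAP 3.7.1).
- ICS window: the 7 days before first dose (SAP 5.6.6), computed here as if from imputed dates.
- Visit 1: 7 to 14 days before first dose (Protocol 3.1, SAP 3.1).
- Assumption: the cap written in rule 4 applies to every imputed start.

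**Step 1: latest start consistent with the protocol.** Four weeks before Visit 1, with Visit 1 at least 7 days before first dose, gives 28 + 7 = 35 days. For a first dose on 20 Sep 2017, a compliant continuing user was on the steroid by 16 Aug 2017.

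**Step 2: rules applied, first dose 20 Sep 2017.**

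| Recorded start | Stop | Imputed start | Prior | Concomitant | In ICS window |
|---|---|---|---|---|---|
| missing | ongoing | 20 Sep 2017 | no | yes | no |
| missing | 25 Jan 2018 | 20 Sep 2017 | no | yes | no |
| 2017 | ongoing | 20 Sep 2017 | no | yes | no |
| Sep 2017 | ongoing | 20 Sep 2017 | no | yes | no |
| Aug 2017 | ongoing | 1 Aug 2017 | yes | yes | yes |
| 2012 | ongoing | 1 Jan 2012 | yes | yes | yes |
| missing | 1 Jun 2017 | 1 Jun 2017 | yes | no | no |

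The first four rows fail for a drug in use before first dose; the last three are right. With first dose on 10 Jan 2018, a missing start on an ongoing drug still fails, but a start known only as 2017 becomes 1 Jan 2017 and is classified correctly.

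**Step 3: who the failing rows can be.** In the year-only row, a compliant user could have started at any time from 1 Jan to 16 Aug 2017. In the month-only row, September cannot be the original start of a compliant user. It can be a new record for a patient moved from a combination product to the steroid alone, as Protocol 5.9.1 provides.

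**Step 4: size, by assumption.** Let *u* be the share of patients truly on ICS, and *m* the share of those whose only ICS record is moved to first dose.

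- Patients affected = 400 × *u* × *m*.
- ICS share shown as prior = *u*(1 − *m*).
- If the subgroup uses imputed dates, the share of true users in the no-use stratum is *c* = *um* / (1 − *u* + *um*).

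| *u* | *m* | Patients affected | *c* |
|---|---|---|---|
| 0.30 | 0.02 | 2.4 | 0.006/0.706 = 0.8% |
| 0.50 | 0.10 | 20 | 0.05/0.55 = 9.1% |
| 0.70 | 0.20 | 56 | 0.14/0.44 = 31.8% |

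In the middle row, the prior table would show 0.50 × 0.90 = 45% on ICS instead of 50%. If the moved users respond like other users, the apparent difference in treatment effect between the strata is about (1 − *c*) times the true one, or 91% in that row.

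**The case against.** Several objections carry weight.

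- **Scope.** A reader might infer that long-standing steroid users in general become non-users. The rules do not support that. An earlier year, or an earlier month and year, is enough for correct classification, and a drug stopped before first dose stays prior through the cap.
- **The subgroup.** A reader might take misclassification of the ICS subgroup as established. SAP 5.6.6 does not say that use is derived from imputed start dates, and SAP 3.8.3 mentions only the prior and concomitant classification. The fair statement is that the derivation is unspecified and that one natural way of programming it would misclassify. The effect on the prior tables does not depend on this.
- **Frequency.** Protocol 5.9.1 asks for start and stop dates and times of COPD therapies, and Protocol 8.3 provides for consistency checks and queries. Missing ICS start dates may be few. The SAP nevertheless provides for wholly missing dates.
- **Consequence.** The drug is not lost, since it remains in the concomitant table. The prior tables are descriptive. ICS is one of seven subgroups.
- **The opposite error.** Sending every incomplete start to the earliest compatible date would turn some drugs begun on treatment into prior drugs. This is right, and it limits the remedy.

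What remains is a written rule that gives a wrong answer for an identifiable set of records, against the protocol's own condition for ICS.

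**Conclusion.** The point stands in a limited form. As written, SAP 3.8.5 misclassifies drugs in use both before and after first dose whose start date is wholly missing or known only to the first-dose year or month. They appear as concomitant only and are missing from the prior and prior-COPD tables. For continuing ICS, the imputed date falls at least 35 days after the latest start that Protocol 5.9.1 allows for a compliant user.

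Movement into the no-use stratum is conditional on the subgroup being built from imputed dates. If it is, the expected result is dilution of any ICS difference, provided incomplete dates are unrelated to treatment arm.

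A reader might also infer that the primary result is at risk. It is not: the model in SAP 5.6.2 and Appendix 4 has no ICS term, so neither the Week 4 contrasts nor the fixed-sequence test changes. The range of about 2 to 56 of 400 patients rests wholly on assumed rates, and the true number may be small.

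**What to change.** In SAP 3.8.5, replace the cross-reference for start dates with a rule for medications:

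- A medication recorded at Visit 1 or pre-dose at Visit 2 with a missing or partial start date is treated as started before first dose (for ICS, before screening), unless the known date parts or the stop date show otherwise.
- A medication first recorded after dosing keeps the current rule. This avoids the opposite error.

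In SAP 5.6.6, classify ICS use from the Visit 1 and Visit 2 medication records covering the final week of run-in, not from imputed start dates.

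Under this rule the four failing example records, if recorded by Visit 2, become prior and concomitant and count as run-in use. The other three do not change.

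The cost is one paragraph in 3.8.5, one sentence in 5.6.6 and the matching programming. No new data are needed: Protocol 7.1.5 has prior COPD therapies recorded at screening, and the schedule of assessments lists prior and concomitant medications at both visits. A count of affected records by arm would show whether the change matters in practice.

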3.9. Interim Analyses and Data Monitoring

There are no planned interim analyses of data from this study.

3.10. Pooled country/region

For all analyses, sites will be pooled within countries. This will be detailed and approved prior to database lock.

4. Patient disposition, demographic and baseline characteristics, medical history, prior and concomitant medications, treatment compliance and exposure

4.1. Patient disposition

The final patient disposition will be presented by treatment group and overall. The total number of patients randomized, treated, completed and discontinued (including reason for discontinuation as recorded on the CRF) from the study will be summarized by treatment group and overall. The total number of patients prematurely discontinued will be presented overall and by visit. If the patient has discontinued between Visit 2 and Visit 3 it will be counted on those discontinued up to Week 1, and so on.

4.2. Demographic and Other Baseline Characteristics

Demographics including age, age group, gender, ethnicity and race will be presented by treatment group and overall. Also, presented by treatment group and overall are the following baseline characteristics: post-bronchodilator FEV1 (both in liters and in percentage of predicted normal), post-bronchodilator FVC, FEV1/FVC, FEV1 reversibility test results, duration of COPD (from diagnosis to randomization), smoking habits.

Statistical testing will not be performed on these parameters.

4.3. Medical History

The number and percentage of patients in the SAF with at least one medical condition, diagnosis or surgery will be presented by treatment group and overall. Furthermore, the incidence for each System Organ Class (SOC) and Preferred Term (PT) will be presented. For each patient, multiple events that map to a SOC and PT will be counted only once for incidence counts. Events will be in descending frequency of SOC and PT in summaries. A listing of all medical history will also be presented.

4.4. Prior COPD, Prior and Concomitant Medications

Prior medications are defined as medications taken prior to first study medication dose. Concomitant medications are defined as medications with onset dates on or after the first dose of study medication, or medications with onset dates prior to first dose of study medication without a stop date or with a stop date after first dose of study medication. Partial date imputation for medications is described in section 3.8.5.

Prior and concomitant medications will be classified by WHO Drug Dictionary that identifies the active ingredient. .

Prior and concomitant medications will be summarized by therapeutic subgroup (ATC level 2), active ingredient and treatment group (for prior COPD medications and prior medications the overall column will also be presented), displaying frequencies and percentages. The denominators for the percentages will be the numbers of patients in each treatment group. Medications will be sorted by decreasing order of frequency of the therapeutic subgroup and active ingredient within subgroup.

A separate summary of patient taking COPD medications prior to the study by therapeutic class will also be presented. COPD medications are identified as those with 'Indication='COPD' on the medication log.

4.4.1. Special grouping of medications

Special grouping of beta agonist will be done as follows and will replace the ATC2 code classification.

- LAMAs

ATC4=R03BB and active ingredient equal to

- tiotropium
- umeclidinium
- aclidinium

ATC4=A03AB and active ingredient equal

- glycopyrronium

- LABAs

ATC4=R03AC and active ingredient equal to

- salmeterol
- formoterol
- indacaterol
- olodaterol

ATC4=R03AK and active ingredient equal to

- vilanterol and fluticasone furoate

ATC4=R03AL3 and active ingredient equal to

- vilanterol and umeclidinium bromide

○ vilanterol, umeclidinium bromide and fluticasone furoate

- Inhaled corticosteroids (ICS)

ATC4 = R03BA or

ATC4= R03AK and active ingredient equal

- beclometasone
- budesonide
- flunisolide
- betamethasone
- fluticasone
- triamcinolone
- mometasone
- ciclesonide
- fluticasone furoate

- LABA/LAMA

Active ingredient includes

- ‘glycopyrronium’ and ‘indacaterol’
- ‘olodaterol’ and ‘tiotropium’
- ‘aclidinium’ and ‘formoterol’
- ‘umeclidinium’ and ‘vilanterol’

- LABA/ICS

Active ingredient includes

- ‘budesonide’ and ‘formoterol’
- ‘fluticasone’ and ‘salmeterol’
- ‘fluticasone’ and ‘vilanterol’
- ‘beclomethasone’ and ‘formoterol’
- ‘mometasone’ and ‘formoterol’

4.5. Exposure and compliance

4.5.1. Treatment Compliance

Treatment compliance will be summarized by treatment group in 2 ways:

1. $100 * ((\text{number of vials dispensed} - \text{number of vials returned}) / (\text{expected number of vials to be taken during study period}))$ (excluding visit 6 for completers, as the vials will be dispensed by the site)
2. Drug intake as recorded in the e-diary: percent of 'yes' responses. The denominator is the number of records for which the patient provided an answer (Yes or No) to drug intake questions (morning and evening) in the e-diary.

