3 INVESTIGATIONAL PLAN

3.1 Overall Study Design and Plan Description

This is a Phase IIb, randomized, double-blind, placebo-controlled, parallel-group study to investigate the effect of nebulized RPL554 in patients with moderate COPD over 4 weeks. It is planned to enroll approximately 400 patients at 45 sites. The study comprises six visits: screening (Visit 1), randomization (Visit 2), and 4 weekly visits (Visit 3 to Visit 6).

Patients will be screened for eligibility (Visit 1), including a reversibility test with albuterol/salbutamol, between 7 and 14 days before the first dose of study medication. After the screening visit, patients will be instructed to wash out any long acting bronchodilators (long acting beta2-agonists [LABA] and/or long acting muscarinic antagonists [LAMA]) but can continue on an inhaled corticosteroid at the same dose. Albuterol/salbutamol may be used on a regular or as needed basis, but must be held for at least 8 hours before a study visit. Albuterol/salbutamol should not be used after administration of study medication for the duration of the clinic visit, unless absolutely necessary for relief of symptoms.

Eligible patients will then return for Visit 2. The pre-dose FEV₁ must be within 20% of the predose FEV₁ at the screening visit. Patients will be assessed for inclusion into the study, and if appropriate will be randomized to one of the five treatment arms. They will receive the first two doses of study medication (RPL554 or placebo) in the clinic (morning and evening) and have spirometry performed for 12 hours. [REDACTED] Patients will be discharged from the clinic, having been instructed to use the study medication on a twice daily basis.

Patients will return for three interim, weekly visits. At each visit, patients will return used and unused study medication and receive new study medication from the unblinded study staff. The first dose of the newly dispensed study medication will be administered in the clinic with spirometry performed for 3 hours after dosing.

At the final study visit (Visit 6), patients will be resident at the study center from the morning until at least 12 hours after dosing to allow for monitoring of lung function and study closeout procedures. A follow-up phone call will occur 2 weeks after the final study visit as a safety follow-up.

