5.3 Preparation and Labelling

5.3.1 Nebulized RPL554 and Placebo

The vials containing RPL554 and placebo will be labelled in compliance with GMP, released by a qualified person (QP), where appropriate, and then shipped to the study center.

For each in-clinic nebulization, an unblinded individual will pour the liquid from the vial into the nebulizer cup and will not disclose the nature (appearance) of the study medication to the blinded Investigator and study staff.

At Visits 2 to 5, patients will be dispensed 20 vials for twice daily dosing over 7 days (six vials provided as extras). For all visits, the first dose will be used for the in-clinic nebulization; for Visit 2 only the second dose will also be given in-clinic. The final dose administered in the morning at Visit 6b (final study visit) will be individually packaged. As such, the study medication administered in the clinic will always be stored only at the study center.

Verona Pharma plc CONFIDENTIAL Page 31 of 67

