5.11 Treatment Compliance

Treatment compliance will be monitored in 3 ways: 1) e-diary, where the number of nebulizations per day will be recorded, 2) the number of returned used vials, and 3) trough pharmacokinetic assessments at Visits 3 and 6.

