4.5.2. Extent of Exposure

Duration of exposure to study medication will be calculated as follows:

$(\text{Stop date} - \text{start date}) + 1$.

The mean duration of exposure in days will be summarized by treatment group. Total exposure (in mL) will be based on the number of vials dispensed against the number returned (number of vials * contents of each vial (in mL)).

For in-clinic dosing, the RPL554 exposure will be calculated based on the nominal dose.

5. Efficacy Endpoints

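### The SAP 4.5.1 vial-compliance formula does not limit returned vials to unused ones, so read literally alongside the protocol it does not measure doses taken

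*SAP*

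**What the plan says.** SAP 4.5.1 gives two compliance measures. The first is 100 × (vials dispensed − vials returned), divided by the "expected number of vials to be taken during study period", leaving out Visit 6 for completers. The subtracted term is the "number of vials returned", with no qualifier, and the SAP does not define it elsewhere. The second measure is the percentage of yes answers on drug intake in the e-diary.

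SAP 4.5.2 reuses the count: "Total exposure (in mL) will be based on the number of vials dispensed against the number returned".

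The protocol describes returns and compliance in several places:

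- Section 3.1, for the three interim weekly visits: "patients will return used and unused study medication".
- Section 6.4.1: at Visits 3 to 5 the unblinded staff collect used and unused medication.
- Section 6.5.1: at Visit 6 only unused medication is named for collection.
- Section 5.6: used and unused vials go back to the sponsor at the end of the study.
- Section 5.11: one of three compliance checks is "the number of returned used vials".
- Section 9.2.2.4: compliance is calculated from used and unused returned vials, together with the e-diary.

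SAP 3.4, which lists changes from the planned analyses, does not mention compliance.

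**The concern.** Dispensed minus returned estimates doses taken only if every returned vial is a full one. The protocol uses the word more widely: empty vials are returned too, and section 5.11 treats them as evidence of dosing. If a programmer takes the SAP formula and the protocol's returns at face value, each used vial that comes back lowers the score. The result then reflects vials that were not returned rather than doses taken.

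What is at stake is the by-arm summary of vial compliance and the total exposure in mL. In a dose-ranging trial these help readers judge whether each arm took its assigned dose. The SAP is marked as the final version for implementation after database lock, so its formulas should not need the programmer to guess which vials are meant.

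**Working it through.** **Inputs**

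- Vials per dispensing: protocol 5.3.1 gives 20 for 7 days of twice-daily dosing, including six extras. Check: 2 × 7 + 6 = 20, which reproduces.
- Dispensings: Visits 2, 3, 4 and 5, so 4 × 20 = 80 vials.
- Expected vials: twice daily for 28 days (protocol 3.3), so 2 × 28 = 56, with the separately packaged Visit 6 dose left out as SAP 4.5.1 directs.
- A full complier therefore has 56 used vials and 80 − 56 = 24 unused ones.
- In-clinic doses from the dispensed boxes: two at Visit 2 and one at each of Visits 3 to 5, so five vials.

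The documents state no compliance percentage to reproduce.

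**Full complier.** Score = 100 × (80 − returned)/56.

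| What is counted as returned | Returned | Score |
|---|---|---|
| All used and unused vials | 80 | 0/56 = 0% |
| As above, less the five in-clinic vials | 75 | 5/56 = 8.9% |
| Used and unused at Visits 3 to 5, unused only at Visit 6 (protocol 6.5.1) | 3 × 20 + 6 = 66 | 14/56 = 25% |
| As above, less the four in-clinic vials from the first three boxes | 62 | 18/56 = 32.1% |
| Used vials only (the count named in protocol 5.11) | 56 | 24/56 = 42.9% |
| Unused vials only | 24 | 56/56 = 100% |

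The two rows that leave out in-clinic vials assume the site does not log those vials as returned. The documents do not say either way.

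**Patient who took 28 of the 56 doses and lost no vials**

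- All vials counted: (80 − 80)/56 = 0%, the same as the full complier.
- Protocol 6.5.1 followed at Visit 6, doses spread evenly at 7 per week: returned = 3 × 20 + 13 = 73, so 7/56 = 12.5%.
- Used vials only: (80 − 28)/56 = 92.9%, higher than the full complier, so the scale runs backwards.
- Unused vials only: (80 − 52)/56 = 50%, the correct value.

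**Lost vials.** A patient who returns nothing scores 80/56 = 143% whatever was taken. This remains true when only unused vials are subtracted.

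**Exposure.** Dose divided by concentration is 2.5 mL in every active arm (0.75/0.3 = 1.5/0.6 = 3.0/1.2 = 6.0/2.4 = 2.5). Assuming that is the vial content, a full complier's 56 vials amount to 56 × 2.5 = 140 mL. If 4.5.2 were implemented as dispensed minus all returned vials, the figure would be 0 mL.

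**The case against.** The best reply is that this is an undefined term rather than faulty arithmetic. The denominator is vials to be taken, so the numerator must be meant as vials taken, and that works only if the returned vials are unused ones. Protocol 6.5.1 also names only unused medication at Visit 6. The accountability fields of the case report form are not in the documents, so the count behind the formula cannot be seen. Scores near zero in every arm, next to the e-diary measure, would be noticed in the first output. Most of this stands, and unused is almost certainly the intended meaning. It does not remove the point, because the stated formula and the protocol's return rules do not fit together, and protocol 9.2.2.4 itself speaks of used vials as returned.

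Four stronger readings are tempting, and the documents do not support them:

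- *Every patient scores 0%, or gets a wrong number.* The 0% needs every used vial to be returned and counted. A patient who returned only the unused vials would be scored correctly.
- *The protocol bases compliance on used vials alone.* Section 5.11 does so for monitoring, but section 9.2.2.4 uses both kinds. The protocol is not uniform.
- *The exposure formula is proven wrong in the same way.* SAP 4.5.2 sets dispensed vials against returned ones without writing a subtraction, and uses the nominal dose for in-clinic dosing. It shares the undefined count and no more than that can be said.
- *The per-protocol set is affected.* SAP 3.6 leaves major deviations to a separate document. Nothing available shows that vial compliance enters it.

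**Conclusion.** The point holds as a definition error of low severity. Taken literally with the protocol's return rules, SAP 4.5.1 gives a full complier 0% if all vials are counted, and 25% if only unused vials are collected at Visit 6. Leaving in-clinic vials out of the returned count changes these to 8.9% and 32.1%. No reading checked that counts returned used vials gives a full complier 100%. These figures rest on 80 vials dispensed, 56 expected and no vials lost.

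The consequence is limited to the descriptive vial-compliance summary and, through the shared count, the exposure summary. The e-diary compliance measure does not use vial counts. The primary repeated-measures analysis on the full analysis set uses neither compliance nor exposure.

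**What to change.** - In SAP 4.5.1, change the subtracted term to the number of *unused* vials returned. State in SAP 4.5.2 that the same count is used.
- Report vials not accounted for (dispensed, but returned neither used nor unused) in a separate line, because the corrected formula counts a lost vial as taken.
- Reconcile protocol 5.11, 6.5.1 and 9.2.2.4 on which vials are collected at each visit and which are counted.

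Used vials returned divided by expected vials is not an equivalent alternative. It treats a lost used vial as a missed dose, and if the five in-clinic vials were not logged as returned a full complier would score 51/56 = 91.1%. One definition should be chosen, and subtracting unused vials keeps the SAP's existing structure.

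The cost is a word in 4.5.1, a clarifying phrase in 4.5.2, one extra summary line and a short protocol clarification. No new data are needed if used and unused counts were recorded separately, as protocol 9.2.2.4 implies.
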